12. PHARMACODYNAMICS

[REDACTED]

The final disposition of samples will be conducted per local regulations.

Details on processes for collection and shipment of these samples can be found in the procedure manual.

CONFIDENTIAL

The information contained herein may not be used, disclosed, or published without the written consent of Biogen MA Inc.

[REDACTED]

14. IMMUNOGENICITY ASSESSMENTS

A validated immunoassay will be used to assay samples for the presence of, and measure titers of, anti-BIIB092 antibodies in serum on an ongoing basis in Study 251PP301. Samples will be collected during the 52-week double-blind period at Day 1, Week 4, Week 8, Week 12, Week 24, Week 36, and Week 48 (Table 2). In addition, samples will also be collected during the open-label extension period approximately every 24 weeks (Table 3). All samples will be collected predose.

Anti-drug antibody (ADA) titers will be monitored throughout the course of Study 251PP301. If ADAs are observed, analyses will be conducted to assess impacts on safety, pharmacological, and efficacy measures across treated participants with and without ADAs. ADAs may also be assessed for neutralizing activity.

Participants who withdraw from Study 251PP301 with ADA titers that are not stable or are increasing in two consecutive samples leading up to discontinuation will be asked to return for follow-up assessment approximately every 6 weeks for up to 24 weeks for measurement of ADAs and immunological AE assessment until resolved (defined as two sequential samples showing no change or declining levels).

Clinically relevant immune reactions (e.g., hypersensitivity reactions) will be treated according to current standard of care medical practice. Additional samples for immunogenicity assessments referred to as “event driven” samples may be justified on the basis of \geq Grade 3 hypersensitivity reactions. The immunogenicity and corresponding drug exposure (PK) data from these samples will be reported as part of a participant’s overall PK and immunogenicity assessment.

CONFIDENTIAL

The information contained herein may not be used, disclosed, or published without the written consent of
Biogen MA Inc.

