Serum Anti-BIIB092 Antibody	X	See notes	X	X			Weeks 4 and 8 only. Additional event driven samples may be justified; see Section 14.
Adverse Event Reporting							
Monitor for Non-Serious Adverse Events (NSAEs)	Collection of NSAEs begins at initiation of study treatment and continues throughout the study and until 30 days following the last dose. Participants who discontinue study treatment should have an assessment of AEs 30 days after last dose. ^e						
Monitor for Serious Adverse Events (SAEs)	Following written consent to participate in the study, all SAEs whether related or not related to study treatment that occur during the screening period, continuously throughout the study, and until 30 days following the last dose, should be monitored and recorded. Participants who discontinue study treatment should have an assessment of SAEs 30 days after last dose. ^e						
Efficacy Assessments							
Progressive Supranuclear Palsy Rating Scale (PSPRS)	X		X	X	X	X	
MDS-UPDRS Part II, CGI, RBANS, PSP-QoL	X		X		X	X	
SEADL, Phonemic Fluency, Letter-Number Sequencing, Color Trails Test, MoCA	X		X	X ^f			

CONFIDENTIAL

The information contained herein may not be used, disclosed, or published without the written consent of Biogen MA Inc.

Procedure ^a	Week 0 (Day 1)	Weeks 4, 8, 16, 20, 28, 32, 40, 44 ^b (±3 days)	Weeks 12, 24, 36 (±3 days)	Week 48 (±3 days)	Week 52 (±3 days)	Early Discontinuation ^{c, d}	Notes
[REDACTED]	■		[REDACTED]	■			[REDACTED]
Magnetic Resonance Imaging (MRI)			See notes		X		Week 24 only.
Lumbar Puncture (LP)					X	X	LP should be performed prior to dosing ([REDACTED]).
Pharmacokinetic (PK) Assessments							
Blood PK Sampling	See notes	See notes	See notes	See notes	See notes		Weeks 0, 4, 24, and 48: collect predose and at EOI. Weeks 12, 36, and 52: collect predose only.
CSF PK Sampling					X	X	Collect at the time of LP ([REDACTED]).
Clinical Study Treatment Supplies							
Randomize	X						Prior to dosing for study treatment vial assignments (call should be made within 1 day prior to dosing).
Dispense Study Treatment	X	X	X	X			Duration of infusion will be at least 1 hour.

AE = adverse event; BP = blood pressure; CSF = cerebrospinal fluid; CGI-C = Clinical Global Impression of Change; CGI-S = Clinical Global Impression of Severity; [REDACTED] ECG = electrocardiogram; EOI = end of infusion; [REDACTED]

CONFIDENTIAL

The information contained herein may not be used, disclosed, or published without the written consent of Biogen MA Inc.

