- ^f CGI interviews collected from Week 36 will be used to review all areas of the functioning section (including complex daily activities and basic functions) and will be used to determine whether there have been any changes or additions to the functioning at the Week 48 visit, with both the caregiver and participant independently. This will be used to assign the Week 48 SEADL score.

CONFIDENTIAL

The information contained herein may not be used, disclosed, or published without the written consent of Biogen MA Inc.

Table 3: Extension Period Procedural Outline

Procedure	Week 52	Weeks 56, 60, 68, 72, 80, 84, 92, 96, 104, 108, 116, 120, 128, 132, 140, 144, 152, 156, 164, 168, 176, 180, 188, and 192 ^a . (±7 days)	Weeks 64, 88, 112, 136, 160, 184 (±7 days)	Weeks 76, 100, 124, 148, 172, 196 (±7 days)	Early Discontinuation ^b	Notes
Eligibility Assessments						
Concomitant Medications	Review of concomitant medication as per Section 7.7 .					
Safety Assessments						
Physical Examination			See notes	X	X	At Week 64 only.
Targeted Physical Examination		X	X	X	X	Post-dose. Targeted, problem-focused physical examination performed at clinician's discretion (e.g., to evaluate any AEs).
Neurological Examination				See notes		Week 100 only. Besides documenting signs of PSP, the NE should focus on any clinical evidence of increased intracranial pressure (e.g., history of headache, vomiting, or visual disturbances, and neurologic signs such as pupillary abnormalities and papilledema) that might contraindicate a lumbar puncture.
Physical Measurements			X	X	X	Weight only.
Vital Signs		X	X	X	X	

CONFIDENTIAL

The information contained herein may not be used, disclosed, or published without the written consent of Biogen MA Inc.

Procedure	Week 52	Weeks 56, 60, 68, 72, 80, 84, 92, 96, 104, 108, 116, 120, 128, 132, 140, 144, 152, 156, 164, 168, 176, 180, 188, and 192 ^a . (±7 days)	Weeks 64, 88, 112, 136, 160, 184 (±7 days)	Weeks 76, 100, 124, 148, 172, 196 (±7 days)	Early Discontinuation ^b	Notes
12-Lead Electrocardiogram (ECG)				X	X	
Assess Infusion site		X	X	X	X	
Laboratory Tests			See notes	X	X	At Week 64 only.
Pregnancy Test		X	X	X	X	For WOCBP only (serum or urine - local/site).
			■	■	■	
Immunogenicity Assessments						
Serum Anti-BIIB092 Antibody ^c				X		Additional event driven samples may be justified; see Section 14.
Adverse Event Reporting						

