5.4. Number of Participants

It is anticipated that approximately 459 male and female participants will be dosed in this study. Approximately 459 participants will be randomly assigned, in 2:1 ratio, to receive 2000 mg of BIIB092 or placebo (306 participants active and 153 placebo) administered by intravenous (IV) infusion approximately once Q4W. Randomization will be stratified by country and screening CTT Part 2 score of either less than or equal to 170 seconds or greater than 170 seconds. Anticipating a dropout rate of approximately 25%, approximately 345 participants (230 participants in the BIIB092 treatment group and 115 participants in the placebo group) are expected to complete the study through Week 52.

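### Protocol Section 14 follows up withdrawing participants on the trend of their last anti-drug antibody samples, but Tables 2 and 3 schedule no antibody sample at Early Discontinuation

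*Protocol*

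**What the plan says.** **The follow-up rule.** Protocol Section 14 covers "Participants who withdraw from Study 251PP301 with ADA titers that are not stable or are increasing in two consecutive samples leading up to discontinuation". They "will be asked to return for follow-up assessment approximately every 6 weeks for up to 24 weeks for measurement of ADAs" and for immunological adverse events.

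**The sampling times.** The same section places double-blind samples "at Day 1, Week 4, Week 8, Week 12, Week 24, Week 36, and Week 48". It adds that "samples will also be collected during the open-label extension period approximately every 24 weeks".

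**The schedules.** The antibody row of Table 2 matches that list; its Week 52 and Early Discontinuation cells are blank, and its note reads "Weeks 4 and 8 only. Additional event driven samples may be justified; see Section 14". The antibody row of Table 3 is marked only for Weeks 76, 100, 124, 148, 172 and 196, is blank at Early Discontinuation, and carries the note "Additional event driven samples may be justified; see Section 14". Both tables mark laboratory tests at Early Discontinuation.

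**Event-driven samples.** Section 14 ties these to hypersensitivity reactions of Grade 3 or higher.

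**Dropout.** Protocol Section 5.4 states: "Anticipating a dropout rate of approximately 25%, approximately 345 participants" are expected to complete through Week 52.

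**Use of the data.** Immunogenicity is a secondary objective (Protocol Section 4). The placebo-controlled SAP (Section 6.2.3) and the extension SAP (Sections 6.2.4 and 6.2.5) compare safety events between participants with and without treatment-emergent ADA.

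**The concern.** The Section 14 rule acts at withdrawal and depends on the titer trend just before it. The visit made at that moment collects laboratory blood but no antibody sample, so the trend has to come from earlier scheduled draws.

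Two things are at stake. The first is the safety rule. A titer that starts to rise after the last scheduled draw does not trigger the follow-up, and someone who leaves before Week 4 has only the Day 1 sample, so no pair of samples exists.

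The second is ascertainment. A participant whose last sample was negative and who seroconverts afterwards is analysed in the group without treatment-emergent ADA, which blurs the comparison of adverse events by antibody status. A participant with no post-dose sample falls outside the ADA population defined in Section 3.2 of the placebo-controlled SAP.

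**Working it through.** **1. Reproduce the plan's figure.** Completers = 459 × 0.75 = 344.25, by arm 306 × 0.75 = 229.5 and 153 × 0.75 = 114.75. These agree with the stated 345 (230 + 115).

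**2. Participants without an exit sample (double-blind).** 459 − 345 = 114, or 114/459 = 24.8%. By arm: 306 − 230 = 76 on BIIB092 and 153 − 115 = 38 on placebo.

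**3. Age of the last sample.** Age = withdrawal week minus the last scheduled draw among Weeks 0, 4, 8, 12, 24, 36 and 48, ignoring visit windows. The largest possible age is about 4 weeks before Week 12 and after Week 48, and about 12 weeks between Weeks 12 and 48. The documents give no distribution of withdrawal times, so one must be assumed.

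*Uniform over 0-52 weeks.*
- Mean age: there are four intervals of 4 weeks and three of 12 weeks, so (4 × 4²/2 + 3 × 12²/2)/52 = (32 + 216)/52 = 4.8 weeks.
- More than 8 weeks old: withdrawal in Weeks 20-24, 32-36 or 44-48, so 12/52 = 23% of dropouts (about 26 people).
- No post-dose sample: withdrawal before Week 4, so 4/52 = 7.7% (about 9 people).

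*Constant hazard with 25% gone by Week 52.* The share still in the study at week t is S(t) = 0.75^(t/52).
- No post-dose sample: (1 − 0.75^(4/52))/0.25 = 0.0219/0.25 = 8.8%.
- More than 8 weeks old: [S(20) − S(24) + S(32) − S(36) + S(44) − S(48)]/0.25 = (0.0196 + 0.0183 + 0.0172)/0.25 = 22%.
- Mean age: 4.7 weeks.

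*Range.* The table uses withdrawal density rising linearly with time (late-weighted) or falling linearly (early-weighted).

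| Withdrawal pattern (assumed) | Mean age, weeks | More than 8 weeks old | No post-dose sample |
|---|---|---|---|
| Early-weighted | 4.0 | 16% | 15% |
| Constant hazard | 4.7 | 22% | 8.8% |
| Uniform | 4.8 | 23% | 7.7% |
| Late-weighted | 5.5 | 30% | 0.6% |

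Percentages are of dropouts. As numbers of people among 114, no post-dose sample runs from about 1 to about 17.

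**4. Extension.** The gap from Week 48 to the next draw is 76 − 48 = 28 weeks; later gaps are 24 weeks. Late-start participants take their first BIIB092 dose at Week 52, so their first sample on drug comes 76 − 52 = 24 weeks later and their second 100 − 52 = 48 weeks later. No extension dropout rate is given. If the double-blind rate carried over, 1 − 0.75^(24/52) = 12.4% would leave before Week 76 with no sample after starting BIIB092. That is about 14 people if all 115 expected placebo completers entered.

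**5. Other provisions that might supply the sample.**
- The return visit at Week 52 encouraged for withdrawn participants (Table 2, footnote d) has no antibody draw.
- Event-driven sampling needs a hypersensitivity reaction of Grade 3 or higher.
- Continued scheduled visits apply to those who stop treatment but stay enrolled (Table 2, footnote c), not to those who withdraw.

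None of these gives a withdrawing participant an exit sample as a matter of course.

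**The case against.** The strongest reply is that the documents are consistent with each other: Section 14 and the two tables name the same sampling weeks, and the rule speaks of samples before discontinuation, not one on the day. With a mean sample age close to one four-week dosing interval in the double-blind period, the last scheduled draw is often a fair proxy. Earlier positives still count, and event-driven sampling covers the most serious hypersensitivity reactions. All of this stands. It makes the point a gap between what the rule needs and what the schedule supplies, not a conflict between passages.

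A reader might also infer more than the documents support:

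- *A quarter of participants have old or absent samples.* The quarter is planned non-completion. It bounds the number lacking an exit sample, and a third of those (38 of 114) are on placebo. Deaths, losses to follow-up and refusals could not supply a sample in any case.
- *The rule cannot work before Week 8 because two post-dose samples are needed.* Section 14 does not say post-dose, so Day 1 and Week 4 form a valid pair.
- *Anyone without a later sample is scored negative.* The ADA population requires a post-dose sample, so those with none are excluded. Misclassification arises only after an earlier negative sample. A positive with no sample 16 or more weeks later is classed as persistently positive (placebo-controlled SAP, Section 8), so missing samples do not all act in one direction.
- *Those who leave are the ones most likely to have an immune reaction.* Nothing in the documents shows this. The 25% comes from earlier PSP studies, and Protocol Section 3.3 describes low immunogenic potential.

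**Conclusion.** The point holds as a cheap and worthwhile improvement. A safety rule keyed to the last antibody samples before withdrawal has no sample at the withdrawal visit, and no other provision fills the gap.

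In the double-blind period the loss is modest: at most 114 participants without an exit sample, with the last draw usually recent. The proportions rest on assumed withdrawal patterns, and the share with no post-dose sample is the most sensitive to them. The case is stronger in the extension, where the 24- and 28-week gaps follow directly from the schedule; only the 12% figure borrows a rate that the protocol does not state for that period.

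The resulting bias in ADA incidence cannot be sized, because the documents give no seroconversion rate. Sample size and power are unaffected.

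**What to change.** Mark Serum Anti-BIIB092 Antibody in the Early Discontinuation column of Tables 2 and 3, drawn with the laboratory blood already scheduled there, and add that visit to the sampling list in Section 14.

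The windows in Table 13 of the placebo-controlled SAP need no change. They run without gaps to the end of the placebo-controlled period, and the windowing approach they refer to (Section 6.1.2) already provides for early discontinuation records.

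The cost is a schedule amendment plus one extra tube and one assay per attended Early Discontinuation visit: at most about 114 in the double-blind period, and fewer in practice.

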15. OTHER ASSESSMENTS

15.1. PSP phenotypes

Based on participant's medical history, Investigators will be asked to provide the participant's clinical phenotype as outlined in the Movement Disorder Society-PSP criteria [[Höglinger 2017](#)].

PSP clinical phenotypes may include the following:

- PSP with predominant Richardson syndrome
- PSP with predominant ocular motor dysfunction
- PSP with predominant postural instability
- PSP with predominant parkinsonism
- PSP with progressive gait freezing
- PSP with predominant frontal presentation
- PSP with predominant speech/language disorder
- PSP with predominant corticobasal syndrome

CONFIDENTIAL

The information contained herein may not be used, disclosed, or published without the written consent of Biogen MA Inc.

16. MEDICAL RESOURCE UTILIZATION AND HEALTH ECONOMICS

Medical resource utilization and health economics data that is associated with medical encounters may be collected in the CRF by the Investigator and study site personnel for all participants throughout the study. Protocol-mandated procedures, tests, and encounters are excluded.

The data collected may be used to conduct exploratory economic analyses and may include:

- Number and duration of medical care encounters, including surgeries, and other selected procedures (inpatient and outpatient),
- Duration of hospitalization (total days length of stay, including duration by wards; e.g., intensive care unit),
- Number and character of diagnostic and therapeutic tests and procedures, and
- Outpatient medical encounters and treatments (including physician or emergency room visits, tests and procedures, and medications).

CONFIDENTIAL

The information contained herein may not be used, disclosed, or published without the written consent of Biogen MA Inc.

17. STATISTICAL CONSIDERATIONS

17.1. Sample Size Determination

Approximately 459 participants will be randomly assigned in a 2:1 ratio to receive BIIB092 or placebo (306 participants in the BIIB092 treatment group and 153 in the placebo group). Anticipating a dropout rate of approximately 25% (based on previous clinical studies in participants with PSP), approximately 345 participants (230 participants in the BIIB092 treatment group and 115 participants in the placebo group) are expected to complete the study through Week 52.

Using a two-sided, two-sample t-test with an alpha level set at 0.05, this sample size will provide 80% power to detect a difference of 3.2 points in the change in PSPRS total score from baseline to Week 52 for BIIB092 relative to placebo, assuming a common standard deviation of 9.95 [Stamelou 2016] in the change in PSPRS total score from baseline to Week 52.

17.2. Populations for Analyses

For purposes of analysis, the following populations are defined:

Population	Description
Enrolled participants	All participants who signed informed consent and were assigned a participant identification number
Randomized participants	Enrolled participants who received a randomization treatment assignment from the Interactive Response Technology (BIIB092 or placebo)
Treated participants	Enrolled participants who received at least 1 dose of study treatment, i.e., blinded therapy (BIIB092 or placebo) or open-label BIIB092
Intention-to-treat (ITT) participants	Randomized participants who received at least 1 dose of blinded study treatment
Cumulative BIIB092-treated participants	All randomized participants who received at least 1 dose of BIIB092 during the double-blind and/or the open-label period.

Additional analysis populations will be defined in the statistical analysis plan.

17.3. Handling of Missing Data

Missing data patterns will be summarized. Percentage of participants who withdrew from the study over time through Week 52 will be summarized and graphically presented by (1) as randomized treatment group and reason for discontinuation, and (2) as randomized treatment group and disease severity (split by the median of baseline PSPRS). Observed mean change from baseline in the primary endpoint will be summarized and graphically presented by treatment group and dropout pattern over time.

Main analyses using a likelihood-based mixed model approach will be based on the assumption of missing at random (MAR). Sensitivity analyses for the primary endpoint will be conducted with missing data imputed by multiple imputation. Specifically, the multiple imputation will be

CONFIDENTIAL

The information contained herein may not be used, disclosed, or published without the written consent of Biogen MA Inc.

performed under the following methods under the framework of missing not at random (MNAR):

- **Copy Differences from Control (CDC):** This pattern mixture model assumes that changes over time in future outcomes in participants who withdraw from all treatment groups are similar to those future changes observed among completers in the control group.
- **Jump to Reference (J2R):** This pattern mixture model assumes that participants withdrawn from all treatment groups would have had outcomes similar to those that were observed among completers (with similar baseline characteristics) in the control group.

In addition, an analysis of covariance (ANCOVA) sensitivity analysis at Week 52 will be conducted for the primary using the last observation carried forward (LOCF) method adjusted by historical progression; that is, missing PSPRS data will be imputed by assuming historical placebo progression (11.24 points/year) [Stamelou 2016] from the visit of the last observation prior to Week 52.

17.4. Statistical Analyses

The statistical analysis plan will be developed and finalized before database lock and will describe the selection of participants to be included in the analyses, and procedures for accounting for missing, unused, and spurious data. Below is a summary of planned statistical analyses of the primary and secondary endpoints.

17.4.1. Efficacy Analyses

Efficacy analyses will be performed using the intent-to-treat participants. Unless stated otherwise, all tests of treatment effects will be conducted at a two-sided significance level of 0.05. The primary efficacy analyses will be for comparative efficacy of BIIB092 to placebo in the double-blind treatment period (including all data through Week 52 for participants discontinuing study treatment during the double-blind period). Details of the efficacy analyses for the open-label extension period will be provided in the statistical analysis plan.

Endpoint	Statistical Analysis Methods
Primary	Changes from baseline in PSPRS will be analyzed using a restricted maximum likelihood (REML)-based Mixed Model with Repeated Measures (MMRM) approach. The principal analysis of the primary endpoint will be a MMRM model that will include treatment, visit, treatment-by-visit interaction, stratification factors as categorical fixed effects, baseline value of PSPRS as a continuous covariate, and baseline value of PSPRS-by-visit interaction. An unstructured covariance matrix will be used to model the within-participant errors. If this analysis fails to converge, the following structures will be tested in this order: the heterogeneous Toeplitz covariance structure, autoregressive model of order 1, and compound symmetric. The first covariance structure yielding convergence will be used.

CONFIDENTIAL

The information contained herein may not be used, disclosed, or published without the written consent of Biogen MA Inc.

Endpoint	Statistical Analysis Methods
	
The treatment comparison of BIIB092 to placebo will be based on the difference in least-squares means with a two-sided 95% confidence interval and p-value.
 
Sensitivity analyses for the primary endpoint will include the following analyses:
 
 • ANCOVA analysis at Week 52 using LOCF adjusted by historical placebo progression: The ANCOVA model will include treatment, stratification factors as categorical effects, and baseline value of PSPRS as continuous covariate. • MMRM analysis with missing data imputed by the CDC multiple imputation method. The specification of the MMRM model based on the imputed data will be the same as the primary MMRM model. • MMRM analysis with missing data imputed by the J2R multiple imputation method. The specification of the MMRM model based on the imputed data will be the same the primary MMRM model. • Responder analysis in which participants with missing data at Week 52 will be treated as non-responders. • Subscales of the PSPRS will be summarized over time descriptively. • Additional analysis may be performed with details specified in the statistical analysis plan.
Key Secondary	
 • If the primary analysis finds that participants treated with BIIB092 performed significantly better than placebo, the key secondary endpoints will be analyzed hierarchically in the following order: MDS-UPDRS Part II, CGI-C, RBANS, and PSP-QoL. • The testing procedure will maintain an alpha level of 0.05 at each level of the hierarchy and ensures the preservation of the overall type I error at 0.05.
Non-Key Secondary	
 • Non-key secondary endpoints will be tested at an uncontrolled alpha level of 0.05 per endpoint. The p-values resulting from these analyses will be considered as nominal and descriptive in nature.
Exploratory	
 • Will be described in the statistical analysis plan.

CONFIDENTIAL

The information contained herein may not be used, disclosed, or published without the written consent of Biogen MA Inc.

